6.5.2 Data Pre-processing

Participant selection

See details in [section 6.6](#).

Endpoint datasets

Create 3 separate datasets for the 3 endpoints

- MDS-UPDRS Part I-III sum score from baseline to Month 18;
- MDS-UPDRS Part III subscale from baseline to Month 18;
- MDS-UPDRS Part III ePD subscore from baseline to Month 18.

If a particular subscale (Part I, II or III) is missing at baseline, then the corresponding data from any available visit prior to randomization will be used instead, i.e. most often data collected at the screening visit ([section 5.1.2.1.5](#)). Participants with missing baseline data for a particular endpoint will be excluded from the corresponding dataset ([section 4](#)).

A description of the items which are part of the MDS-UPDRS Part III subscale are presented in [Table 6.2](#). All items are originally scored on a 5-point Likert scale: '0: No problems', '1: Slight', '2: Mild', '3: Moderate', and '4: Severe'. The ePD subscore selected is the 15-item set, which contains all 5 Rigidity items (3.3), Finger tapping (3.4, Right/Left), Hand movements (3.5, Right/Left), Pronation-supination of the hands (3.6, Right/Left), Toe tapping (3.7, Right/Left), and Leg agility (3.8, Right/Left). The ePD subscore will be constructed by summing the score for the 15 items.

Table 6-2: Items to be included in the 15-item MDS-UPDRS Part III ePD subscore

Item	Description	15-item set
3.1	Speech	
3.2	Facial expression	
3.3	Rigidity in the joints	
	Neck	
	Upper joints/extremities (Right/Left)	
	Lower joints/extremities (Right/Left)	
3.4	Finger tapping (Right/Left)	
3.5	Hand movements (Right/Left)	
3.6	Pronation-supination movements of hands (Right/Left)	
3.7	Toe tapping (Right/Left)	
3.8	Leg agility (Right/Left)	
3.9	Arising from chair	
3.10	Gait	
3.11	Freezing of gait	
3.12	Postural stability	
3.13	Posture	
3.14	Global spontaneity of movement	

Table 6–2: Items to be included in the 15-item MDS-UPDRS Part III ePD subscore

Item	Description	15-item set
3.15	Postural tremor (amplitude) of the hands (Right/Left)	
3.16	Kinetic tremor (amplitude) of the hands (Right/Left)	
3.17	Rest tremor amplitude	
	Lip/Jaw	
	Upper limb/extremity (Right/Left)	
	Lower limb/extremity (Right/Left)	
3.18	Constancy of rest tremor	

Steps described in [sections 6.5.3](#) to [6.5.7](#) below will be performed for each of the 3 datasets separately.

For all relevant procedures, the seed will be set to **2024**, at the level of the SAS procedure statement.

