6.5.4 Handling of Missing Data

Intermittent missing data, i.e., missing values for a given subject that has available data before and after the missing time point, will always be assumed to be MAR.

Longitudinal/monotone missing data, i.e., where all subject data is missing after a given time point, can fall into 2 categories, MAR or MNAR (also refer to [section 6.5.3](#)).

Briefly, longitudinal/monotone missing data from participants who discontinued the study for reasons unrelated to randomized treatment or who are lost to follow-up (due to unknown reasons by definition) will be imputed assuming MAR; longitudinal/monotone missing data from participants who discontinued the study for reasons related to randomized treatment (i.e. due to

lack of efficacy) will be imputed assuming missing MNAR, using RBI, here control-based pattern imputation (LingLing, 2019).

Imputation will be applied separately to each **B** bootstrap data samples. A set of **M = 10** imputations per bootstrap data sample will be generated.

For all imputation approaches, time will be set to planned (rather than actual) visit time, i.e. 0, 2, 4, 6, 8, 10, 12, 14, 16 and 18 months, as actual visit time since baseline visit cannot be derived for participants with missing longitudinal/monotone data. Month 18 visit will be set as reference.

Imputation of intermittent MAR data will be implemented using multiple imputation (MI) via Markov Chain Monte Carlo (MCMC) and applying monotone regression (MI-MCMC using the SAS PROC MI procedure with methods/statements MCMC, VAR, with options IMPUTE = monotone and CHAIN = multiple).

Imputation of longitudinal/monotone MAR data will be implemented using MI-MCMC and applying monotone regression (SAS PROC MI procedure with methods/statements MCMC, VAR and MONOTONE REG)

Imputation of longitudinal/monotone MNAR data will be implemented using MI-MCMC, and applying monotone regression but specifying that only observations collected under placebo are to be used to derive the imputation, i.e. RBI (SAS PROC MI procedure with methods/statements MONOTONE REG and MNAR = model).

- For each **B** bootstrap sample, subsets will be created according to each randomized treatment arm, i.e. 3 subsets.
 - Symptomatic treatment (ST) status will be ignored to avoid creating groups with too low sample size for reliable MI.
- MI will be applied to each bootstrap sample subsets separately.
- For each **B x 3** bootstrap sample subset:

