 - And for ALL participants, the intermittent missing values will be filled in using the MI-MCMC method, with a total of **M=10** sets of imputations being performed, using data from the same randomized treatment arm subset;
 - For participants randomized to active treatment with monotone MAR data or participants randomized to Placebo, missing data will be imputed by applying monotone regression on these 10 intermittent missing-imputed subsets, using data from the same randomized treatment arm subset;
For participants randomized to active treatment with monotone MNAR data, missing data will be imputed by applying monotone regression on these 10 intermittent missing-imputed subsets, using data from the randomized placebo arm subset. If any issues are encountered using the monotone MI assuming MNAR approach, a monotone MI assuming MAR approach will be used instead.

Imputed dataset from participants with monotone MAR and MNAR data will be stacked back together to reconstitute the full list of trial participants for each imputed set.

- For each **B** bootstrap sample, the **M**-imputed randomized treatment arm subsets will be stacked again into **M** complete imputed datasets corresponding to a single bootstrap sample (full trial).
- If values outside of the pre-defined range of values for MDS-UPDRS endpoints (defined as the minimum and maximum values which could be observed) are imputed, they will be reset to the relevant lower or upper limit of the range after completion of the MI procedure
 - MDS-UPDRS Part I-III sum score: 0 – 236
 - MDS-UPDRS Part III subscale: 0 – 132
 - MDS-UPDRS Part III subscore: 0 – 60
 - MDS-UPDRS Part II subscale: 0 – 52
 - MDS-UPDRS Part I subscale: 0 – 52

At the end of the imputation process, **B x M** complete datasets will be available.

For all imputation models, sex (reference = Male), age at informed consent signing (agegrp4, reference = 60-69), and geographic region (reference = Europe) will be included as baseline demographics. No missing data is expected for baseline demographics. MI models will only allow continuous variables. Therefore, categorical variables will be re-coded as indicator variables as follows:

Baseline demographics (included in all analyses)

- For sex: Male = 0, Female = 1
- For age at informed consent: 60-69 = 0, 40-49 = 1, 50-59 = 2, 70+ = 3
- For geographic region: Europe = 0, North America = 1

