 - $L_t(s)$, the participant's time-varying variables measured at V_t (generates e.g. lag1updrs2, lag2updrs2 ...).
 - For each $B \times M$ imputed dataset, carry forward participant's demographics L_1 measured at screening/baseline across all visits (generates e.g. lagSex ...)
 - Exclude baseline rows ($t = 1$) from dataset.
- Step 1: Propensity model - For each $B \times M$ dataset, estimate the participant's propensity score (p_t), i.e. the probability of initiating ST at any post-baseline visit based on outcome using a logistic regression model.
 - Exclude rows corresponding to $V_{t=T}$ (i.e. Month 18), where S_t is not applicable
 - Retain rows where S_{t-1} (lag1S) = 0 (i.e. participants did not initiate ST up to and including V_t)
 - Run a logistic regression of S_t on Y_t , adjusting for:
 - V_t , R (Randomized treatment arm) - Class variables as Fixed effects:
 - Sex, Age group, and Geographic region - Class variables as demographics covariates

- MDS-UPDRS Part II, DaT-SPECT striatum SBR - Continuous variables as baseline covariates
- Use model to predict the p_{st} for each participant at each V_t .
 - Where S_{t-1} (lag1S) = 1 or S_t not applicable, then set $p_{st} = 1$;
- Lag the p_{st} variable within each participant, over each V_t as described in the data preparation section above (lag1PS to lagTPS).
- Step 2: linear structural mean model (LSMM) - For each $\mathbf{B} \times \mathbf{M}$ dataset, estimate the lag effects ψ_g of initiating ST between V_t and V_{t+1} on Y_{t+g} for all possible lags g from 1 to G ($T-1$), assuming ψ_g is time-invariant, by implementing a series of linear regression models and de-mediate the overall lag effects of ST on outcome:

To estimate ψ_1 (example for lag $g = 1$),

- Retain rows Y_{t+1} where S_{t-1} (lag2S) = 0 for $t = 1, \dots, T-1$
- Run a linear regression of Y_{t+1} on 1-lag outcome Y_t (lag1Y), observed ST initiation S_t (lag1S), and propensity score for ST initiation p_{st} (lag1PS), adjusting for:
 - R (Randomized treatment arm) - Class variables as Fixed effects (Visit not included as fixed effect):
 - Sex, Age group, and Geographic region - Class variables as demographics covariates
 - MDS-UPDRS Part II, DaT-SPECT striatum SBR - Continuous variables as baseline covariates
- Set ψ_1 estimate equal to the linear coefficient of S_t (lag1S)

To estimate ψ_g for $g = 2, \dots, T-1$ (generalization to all possible lags)

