- Retain rows \tilde{Y}_{t+g} where S_{t-1} (lag(g+1)S) = 0 for $t = 1, \dots, T-g$
- Run a linear regression of \tilde{Y}_{t+g} on g -lag outcome Y_t (laggY), observed ST initiation S_t (laggS), and propensity score for ST initiation p_{st} (laggPS), adjusting as above, for $t = 1, \dots, T-g$ in a single step
- Set ψ_g estimates equal to the linear coefficients of S_t (laggS)

- Step 3: obtain de-mediated outcome data points

- Peel off lag effect ψ_1 from outcome Y_{t+1} to obtain the *1-lag de-mediated* outcome:
$$\hat{Y}_{t+1} = Y_{t+1} - \psi_1 \times \text{lag1S} \quad \text{for } t = 1, \dots, T-1$$
- Update \hat{Y}_{t+g} to sequentially remove all lag effects:
$$\tilde{\hat{Y}}_{t+g} = \hat{Y}_{t+g} - \psi_g \times \text{laggS} \quad \text{for } t = 1, \dots, T-g$$

In practice, \hat{Y}_{t+g} will only be updated where $\text{laggS} = 1$

6.5.6

End-of-trial Analysis Models

Repeated measures model

A mixed effect model (MEM) for longitudinal analysis of covariance (ANCOVA)/repeated measures will be applied to each $\mathbf{B} \times \mathbf{M}$ bootstrapped/imputed/ST de-mediated dataset to obtain $\mathbf{B} \times \mathbf{M}$ mean differences (i.e., $\theta_{b,m}$, see [section 6.5.7](#)) at Month 12 and Month 18 - as required per MDS-UPDRS endpoint – using all data recorded up to Month 12/Month18, respectively.

Treatment, time (visit, categorical) and treatment by time (interaction term between treatment and visit) will be fitted as fixed effects, gender, age at Baseline and respective Baseline MDS-UPDRS data will be fitted as covariates. A heterogenous auto-regressive (ARH1) variance-covariance matrix will be fitted to account for the repeated measures within subject (SAS PROC MIXED with REPEATED statement). Kenward and Roger adjustment will be used to obtain degrees of freedom. For further details, refer to [Section 5.3.1.4.1](#).

Slope model

A LMEM (random coefficients model) for longitudinal data will be applied to each of the $B \times M$ bootstrapped/imputed/ST de-mediated dataset to obtain $B \times M$ mean differences (i.e. $\theta_{b,m}$, see [section 6.5.7](#)) in slope over 12 and/or 18 months - as required per MDS-UPDRS endpoint – using all data recorded up to Month 12/Month18, respectively.

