6.6 Appendix 6: Key inclusion/exclusion criteria for the FAS definition

Participants who did not meet the key inclusion criteria stated below will be excluded from the FAS:

Protocol Criterion 1a: Study participant's age at baseline must be >39 and <76 years, i.e. Study participant must be 40 to 75 years of age inclusive, at the time of signing the informed consent.

Protocol Criterion 2a: Study participant has PD, with a diagnosis made by a neurologist according to the 2015 Movement Disorder Society criteria within 2 years of Baseline Visit (including diagnosis during Screening), at the time of signing the informed consent.

In practice, this be implemented by excluding participants with a disease duration greater than 27 months (3 months over the protocol-defined threshold).

Protocol Criterion 4b: A Screening DaT-SPECT, or a historical DaT-SPECT within 3 months of the Screening Visit (V1) that has been qualified by the central reader, shows evidence of dopamine transporter deficit per study requirements (refer to Section 4.2 of the protocol) and as determined by a central reader.

Protocol Criterion 6a: Study participant is in the ≤ 2.5 modified Hoehn and Yahr stage at Screening.

Criterion 7a. Study participant has never taken medications for the treatment of motor symptoms of PD and is not expected to require starting ST with a high likelihood in the next 6 months as far as clinical judgement allows.

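### SAP 6.5.4 promises indicator variables for age in the imputation models but lists one 0–3 code out of age order; write out three 0/1 indicators

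*SAP*

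**What the plan says.** SAP 6.5.4 (Handling of Missing Data) sets the covariates for the imputation step. It begins "For all imputation models, sex (reference = Male), age at informed consent signing (agegrp4, reference = 60-69" and adds geographic region. It then states "MI models will only allow continuous variables. Therefore, categorical variables will be re-coded as indicator variables as follows", and lists male 0 / female 1, Europe 0 / North America 1 and, for age, "For age at informed consent: 60-69 = 0, 40-49 = 1, 50-59 = 2, 70+ = 3".

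The longitudinal missing-at-random (MAR) data are imputed with the "SAS PROC MI procedure with methods/statements MCMC, VAR and MONOTONE REG". SAP 6.5.2 says the steps in 6.5.3 to 6.5.7 "below will be performed for each of the 3 datasets separately", that is, for the Part I-III sum score, the Part III subscale and the Part III ePD subscore. SAP 6.5.1 lists ten de-mediated estimands on these endpoints: five means and five slopes. Table 1-2 labels the Part III and ePD means as key secondary.

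The later steps treat age differently. SAP 6.5.5 (g-estimation) uses "Sex, Age group, and Geographic region - Class variables as demographics covariates". SAP 6.5.6 (end-of-trial models) says, for the repeated-measures model, "gender, age at Baseline and respective Baseline MDS-UPDRS data will be fitted as covariates"; its slope model also uses age at Baseline.

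**The concern.** A two-level variable coded 0/1 is a true indicator, so sex and region are fine. Four age groups need three indicators, and 6.5.4 defines none. A single 0–3 variable in a continuous-only model gets one slope, and these codes do not follow age. A programmer who follows the mapping fits a model that no clinical reading supports. One who follows the word for indicators departs from the mapping.

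The text has to be unambiguous because the sponsor's own team programs these estimands from this appendix. They also carry interpretive weight. The SAP Amendment 3 rationale says that censoring after ST start is no longer considered unbiased, because so many participants started ST before Month 12. With B = 200 bootstrap samples and M = 10 imputations, 200 × 10 = 2000 datasets per endpoint would be built with this covariate. SAP 6.5.4 also imputes missing baseline Part II and DaT-SPECT values in the same way as intermittent missing data.

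**Working it through.** The plan states no figure to reproduce here, so the check is on the coding itself.

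**1. What the code allows.** Let b be the slope on the listed code.

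| Age group | Listed code | Fitted age effect | Indicators for 40-49, 50-59, 70+ |
|---|---|---|---|
| 40-49 | 1 | b | 1, 0, 0 |
| 50-59 | 2 | 2b | 0, 1, 0 |
| 60-69 | 0 | 0 | 0, 0, 0 |
| 70+ | 3 | 3b | 0, 0, 1 |

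If the outcome rises or falls steadily with age, 40-49 and 70+ must lie on opposite sides of 60-69. With the listed code both lie on the same side for every b other than 0. So no value of b can represent a steady age trend.

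**2. How much of a linear age trend it captures.** Inputs are group midpoints 45, 55, 65 and 73. The last uses the upper limit in "Study participant must be 40 to 75 years of age inclusive, at the time of signing the informed consent" and is rounded up from 72.5. The documents give no age distribution, so the age mix is assumed and varied.

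With equal groups, mean age is 59.5 and mean code 1.5.
- Cross-products: (−14.5)(−0.5) + (−4.5)(0.5) + (5.5)(−1.5) + (13.5)(1.5) = 7.25 − 2.25 − 8.25 + 20.25 = 17.0.
- Sums of squares: age 210.25 + 20.25 + 30.25 + 182.25 = 443; code 0.25 + 0.25 + 2.25 + 2.25 = 5.
- Correlation: 17 / √(443 × 5) = 0.36; squared, 0.13.

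Using age rank 1–4 in place of midpoints gives 2 / √(5 × 5) = 0.40.

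| Assumed mix, youngest to oldest (%) | Correlation of code with age | Share of linear trend captured |
|---|---|---|
| 25/25/25/25 | 0.36 | 13% |
| 5/20/45/30 | 0.30 | 9% |
| 10/25/40/25 | 0.22 | 5% |
| 15/35/35/15 | 0.05 | 0.3% |
| 10/30/45/15 | 0.00 | 0% |
| 20/35/35/10 | −0.06 | 0.4% |

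A code in age order captures more than 99% in each mix. Over 20,000 random mixes the median share was 4%, and the correlation was negative in 28%.

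**3. Effect on imputed values.** A simulation imputed Month 18 by regression on the Baseline score plus the age term. Assumptions: mix 10/25/40/25%, age effect 0.2 points per year, dropout rising with age (logit slope 0.05 per year).

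| Age term | Mean error of imputed values, 40-49 / 50-59 / 60-69 / 70+ | Error in whole-arm mean |
|---|---|---|
| Listed code | +3.3 / +1.5 / −1.0 / −1.9 | −0.16 |
| None | +3.3 / +1.3 / −0.7 / −2.3 | −0.17 |
| Three indicators | at most 0.09 in size | −0.01 |

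The listed code behaves almost as if age were left out. This set-up omits the visits between Baseline and Month 18, so it overstates what the planned imputation would do.

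**4. Effect on the treatment difference.** A second simulation imputed within arm, visit by visit, on all earlier scores. It used the SAP Table 3-1 variances, 150 per arm, a 30% slope effect and 1500 runs. Assumptions: the same age mix, about 22–24% missing at Month 18, dropout rising with age. Errors in points, listed code v three indicators:

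| Assumed age effect | Treatment difference | Arm mean |
|---|---|---|
| 0.2 per year on level only | 0.028 v 0.028 | −0.02 v −0.02 |
| plus 0.01 per month per year of age on slope | 0.012 v 0.010 | −0.10 v −0.02 |
| plus 0.02, with steeper age-related dropout | 0.051 v 0.062 | −0.25 v −0.03 |

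The two codings differ in the treatment difference by 0.000, 0.002 and 0.011 points. For scale, the planned effect of 0.27 points per month is 0.27 × 18 = 4.86 points at 18 months if linear. This simulation used deterministic imputation and no dropout pattern that links age and arm. Such a pattern could give a larger effect.

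**The case against.** The strongest reply is that the text already points to indicators. It uses that word and names 60-69 as reference, which makes sense only for indicator or class coding and explains why 60-69 comes first with code 0. SAP 6.5.5 repeats the same reference and fits age group as a class variable. On that reading the list gives level labels and the step to indicators was left out. This is probably what was meant, and it stands as an account of intent. It does not rescue the text: the sentence introduces the list as the recoding itself, and the list is a single variable.

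The second reply is that little depends on it. Imputation conditions on the participant's earlier scores, sex, region, Part II and DaT-SPECT. The coding is the same in every arm, and apart from the reference-based cases for lack of efficacy the imputation is done within arm, so errors largely cancel. This also stands, and it limits the size of the point.

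Two stronger readings are tempting. A reader might infer that the MAR assumption is not implemented. The documents do not support that: the SAP never states MAR as conditional on age alone, and the other predictors remain in the model. What is lost is the age effect beyond those predictors. A reader might also infer that the trial's age adjustment as a whole is wrong. It is not: the primary estimand uses a likelihood model without multiple imputation, and the g-estimation and final models take age in their own form. Only imputed values that feed into those later steps carry the code.

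**Conclusion.** The point holds as a specification error in one step. SAP 6.5.4 states a rule (indicators against 60-69) and then lists a recoding that does not carry it out. Followed as listed, the imputations behind all ten de-mediated estimands lose most of the intended age adjustment: 87% to 100% of a linear trend in the six mixes tried.

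The consequence for treatment differences is probably very small, about 0.01 point or less between codings in the scenarios simulated. Arm means could be off by more, up to about 0.25 points there. Imputed values for a given age group could be off by up to about 3 points when only Baseline is conditioned on. All of these sizes rest on assumed age mixes, age effects and dropout. The documents give none of the three for this population by age, so the true size cannot be fixed. The case for correcting the line rests on the contradiction in the text, not on a demonstrated bias.

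**What to change.** In SAP 6.5.4, replace the age line with three 0/1 variables: 40-49 (yes = 1), 50-59 (yes = 1) and 70+ (yes = 1), with 60-69 as the group where all three are 0. This carries out the SAP's own wording and matches the class coding in 6.5.5. Age in years is an acceptable alternative: it is already continuous and needs one slope.

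The cost is one line of SAP text and one changed variable (or three in place of one) in the imputation calls. No new data are needed, and the SAP expects no missing baseline demographics. It should be done before unblinding.

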6.5.5 ST de-mediation via g-estimation

A g-estimation approach will be implemented on each of the **B x M** imputed complete dataset, to de-mediate the MDS-UPDRS data from the confounding effect of the rescue medication (i.e. ST, Levodopa mainly) on the observed effect of the active randomized treatment (Minzasolmin/UCB0599) to obtain the direct effect of this active treatment.

The basic idea of apply a g-estimation algorithm is to “peel off” the effect of ST on all future MDS-UPDRS observations.

Complete post-MI-MCMC MDS-UPDRS Part I-III sum score, Part III subscale and Part III ePD subscore outcome data will be used in the g-estimation models, both as the dependent variable and as the respective lagged outcomes, i.e. time-varying covariate.

Note that to be conservative, RBI data from participants who discontinued the study for reasons related to randomized treatment will not be ST de-mediated.

In the g-estimation approach, sex (reference = Male), age at formed consent signing (agegrp4, reference = 60-69), and geographic region (reference = Europe) will be included as baseline demographic covariates and carried over time. Baseline/screening data for MDS-UPDRS Part II and DaT-SPECT Striatum SBR (not mean-centered) will also be included as time-varying covariates. Where post-baseline data for these time-varying covariates are missing, a last observation carried forward (LOCF) approach will be applied to impute missing data, both in the case where the variable is not measured at a visit by design, or in the case where it is truly missing (assumes MAR).

Exploratory sensitivity analyses may be run where additional time-varying covariates are included in the g-estimation model as lagged predictors (details to be included in the exploratory analysis plan).

- Prepare dataset for g-estimation 2-step modeling:
 - Set time t to start at 1 up to T (where $T = 10$ visits, Baseline, Month 2 ... Month 18)
 - For each $B \times M$ imputed dataset (including any baseline/post-baseline variables as required), within each participant, lag the following variables over each Visit V_t using SAS functions Lag1, Lag2 to Lag($T-1$), i.e.:
 - S_t , whether a participant initiates ST between V_t and V_{t+1} , set to 1 if yes, set to 0 otherwise (generates lag1S, lag2S ...); once a participant has initiated ST, it is assumed they stay on ST for the remaining of the trial;
 - Y_t , the participant's outcome measured at V_t (generates lag1Y, lag2Y ...)
 - $L_t(s)$, the participant's time-varying variables measured at V_t (generates e.g. lag1updrs2, lag2updrs2 ...).
 - For each $B \times M$ imputed dataset, carry forward participant's demographics L_1 measured at screening/baseline across all visits (generates e.g. lagSex ...)
 - Exclude baseline rows ($t = 1$) from dataset.
- Step 1: Propensity model - For each $B \times M$ dataset, estimate the participant's propensity score (p_t), i.e. the probability of initiating ST at any post-baseline visit based on outcome using a logistic regression model.
 - Exclude rows corresponding to $V_{t=T}$ (i.e. Month 18), where S_t is not applicable
 - Retain rows where S_{t-1} (lag1S) = 0 (i.e. participants did not initiate ST up to and including V_t)
 - Run a logistic regression of S_t on Y_t , adjusting for:
 - V_t , R (Randomized treatment arm) - Class variables as Fixed effects:
 - Sex, Age group, and Geographic region - Class variables as demographics covariates

- MDS-UPDRS Part II, DaT-SPECT striatum SBR - Continuous variables as baseline covariates
- Use model to predict the p_{st} for each participant at each V_t .
 - Where S_{t-1} (lag1S) = 1 or S_t not applicable, then set $p_{st} = 1$;
- Lag the p_{st} variable within each participant, over each V_t as described in the data preparation section above (lag1PS to lagTPS).
- Step 2: linear structural mean model (LSMM) - For each $\mathbf{B} \times \mathbf{M}$ dataset, estimate the lag effects ψ_g of initiating ST between V_t and V_{t+1} on Y_{t+g} for all possible lags g from 1 to G ($T-1$), assuming ψ_g is time-invariant, by implementing a series of linear regression models and de-mediate the overall lag effects of ST on outcome:

To estimate ψ_1 (example for lag $g = 1$),

- Retain rows Y_{t+1} where S_{t-1} (lag2S) = 0 for $t = 1, \dots, T-1$
- Run a linear regression of Y_{t+1} on 1-lag outcome Y_t (lag1Y), observed ST initiation S_t (lag1S), and propensity score for ST initiation p_{st} (lag1PS), adjusting for:
 - R (Randomized treatment arm) - Class variables as Fixed effects (Visit not included as fixed effect):
 - Sex, Age group, and Geographic region - Class variables as demographics covariates
 - MDS-UPDRS Part II, DaT-SPECT striatum SBR - Continuous variables as baseline covariates
- Set ψ_1 estimate equal to the linear coefficient of S_t (lag1S)

To estimate ψ_g for $g = 2, \dots, T-1$ (generalization to all possible lags)

- Retain rows \tilde{Y}_{t+g} where S_{t-1} (lag(g+1)S) = 0 for $t = 1, \dots, T-g$
- Run a linear regression of \tilde{Y}_{t+g} on g -lag outcome Y_t (laggY), observed ST initiation S_t (laggS), and propensity score for ST initiation p_{st} (laggPS), adjusting as above, for $t = 1, \dots, T-g$ in a single step
- Set ψ_g estimates equal to the linear coefficients of S_t (laggS)

- Step 3: obtain de-mediated outcome data points

- Peel off lag effect ψ_1 from outcome Y_{t+1} to obtain the *1-lag de-mediated* outcome:
$$\hat{Y}_{t+1} = Y_{t+1} - \psi_1 \times \text{lag1S} \quad \text{for } t = 1, \dots, T-1$$
- Update \hat{Y}_{t+g} to sequentially remove all lag effects:
$$\tilde{\hat{Y}}_{t+g} = \hat{Y}_{t+g} - \psi_g \times \text{laggS} \quad \text{for } t = 1, \dots, T-g$$

In practice, \hat{Y}_{t+g} will only be updated where $\text{laggS} = 1$

6.5.6

End-of-trial Analysis Models

Repeated measures model

A mixed effect model (MEM) for longitudinal analysis of covariance (ANCOVA)/repeated measures will be applied to each $\mathbf{B} \times \mathbf{M}$ bootstrapped/imputed/ST de-mediated dataset to obtain $\mathbf{B} \times \mathbf{M}$ mean differences (i.e., $\theta_{b,m}$, see [section 6.5.7](#)) at Month 12 and Month 18 - as required per MDS-UPDRS endpoint – using all data recorded up to Month 12/Month18, respectively.

Treatment, time (visit, categorical) and treatment by time (interaction term between treatment and visit) will be fitted as fixed effects, gender, age at Baseline and respective Baseline MDS-UPDRS data will be fitted as covariates. A heterogenous auto-regressive (ARH1) variance-covariance matrix will be fitted to account for the repeated measures within subject (SAS PROC MIXED with REPEATED statement). Kenward and Roger adjustment will be used to obtain degrees of freedom. For further details, refer to [Section 5.3.1.4.1](#).

Slope model

A LMEM (random coefficients model) for longitudinal data will be applied to each of the $B \times M$ bootstrapped/imputed/ST de-mediated dataset to obtain $B \times M$ mean differences (i.e. $\theta_{b,m}$, see [section 6.5.7](#)) in slope over 12 and/or 18 months - as required per MDS-UPDRS endpoint – using all data recorded up to Month 12/Month18, respectively.

MDS-UPDRS will be the dependent variable, Baseline MDS-UPDRS data will be part of the dependent variable rather than a covariate in the model. Time since Baseline in months - as a continuous variable - and the treatment by time interaction (fixed slope) will be fitted as fixed effects, gender and age at Baseline will be fitted as covariates. A fixed effect for treatment will NOT be included in this model. To adjust for the correlation between repeated observations from each participant, a participant-specific random intercept and a participant-specific random slope for time will be fitted as random effects (SAS PROC MIXED with RANDOM statement with option type = UN Kenward and Roger adjustment will be used to obtain degrees of freedom. For further details, refer to [Section 5.3.1.4.1](#).

